### 5.3 Risks and Benefits

The intended clinical benefit of UNITY VCS is to aid in the execution of anterior and posterior segment ophthalmic surgery which include the removal of the opacified, cloudy crystalline lens and to manage vitreoretinal disease. In comparison with predecessor systems, the UNITY VCS provides enhancements that are designed to benefit patients. The UNITY VCS has many enhancements in key areas including fluidics, energy delivery, higher vitrectomy cut speed and allowing greater use of higher gauge sizes. Use of higher gauge sizes may reduce time to close incision, lower surgically induced astigmatism, provide quicker VA improvements, less change in IOP, decreased hypotony, and less need for sutures (Lubiński 2020, and Saleh 2020). UNITY VCS innovations have made design enhancements to the illumination output, viscous fluid control as well as vitrectomy and laser probes to overcome some of the reduction in efficiency currently observed with smaller gauge vitreoretinal surgery (Lee 2023). Higher vitrectomy cut speed in both clinical and simulated settings may improve safety by reducing retinal traction and improve efficiency due to greater aspiration flow (Doi 2023, Steel 2022). The fluidics enhancement was designed with the intent to allow improved control of flow for vitreous cutting and surgeons to operate at lower IOP and higher vacuum while maintaining chamber stability. In specific, operating at lower, more physiological IOP may be associated with greater reported patient comfort during surgery (Hou 2012), improved visual recovery due to better preservation of corneal endothelial health, and less macular edema postoperatively (Suzuki 2009, Chen 2012) as well as reduced complications due to less impact on retinal blood flow/reduction of ischemia (Findl 1997, Takhtaev 2019). The ultrasound energy enhancement was designed to improve crystalline lens cutting efficiency and reduce energy. The overall potential benefit would be a safer and more efficient procedure.

The clinical investigation process risks are managed through appropriate training and monitoring according to the protocol-specific monitoring plan. [REDACTED]

Complications may occur on the surgery day or throughout the postop period. As with any type of intraocular surgery, there is a possibility of complications due to anesthesia, drug reactions, and/or surgical problems. The surgical procedure can exacerbate a preexisting ocular condition

and can also lead to potential procedure related postop adverse events. [REDACTED]

[REDACTED]

[REDACTED]

In addition, a secondary surgical intervention (SSI) may be required following the initial surgery. SSIs include, but are not limited to vitreous aspirations, iridectomy for pupillary block, wound leak repair, intracameral and intravitreal antibiotic injections, additional posterior segment surgery including retinal detachment repair, and pars plana vitrectomy.

All the above-mentioned complications, adverse events, SSIs, and postoperative reported events have been reported because of the ophthalmic surgical procedures with use of a combined anterior and posterior segment surgical system. The UNITY VCS, the investigational device, is not expected to increase any harms or the likelihood of those harms when compared to predecessor devices. [REDACTED]

[REDACTED]. Any risk to subjects in this clinical study will be minimized by compliance with the eligibility criteria and study procedures, and by clinical oversight and monitoring.

The UNITY VCS is expected to provide greater benefits and no additional harms or likelihood of harms when compared to the widely and successfully marketed predecessor devices, the CENTURION and CONSTELLATION Vision Systems. As such, the expected benefits of using the UNITY VCS anterior and posterior segment functions are expected to outweigh the risks of ADEs for subjects that qualify for cataract surgery in this study.

Refer to the IB for additional information.

## 6 STUDY OBJECTIVES

### 6.1 Primary Objective(s)

Table 6-1

Primary Objective(s)

[figure not shown]
Objective(s)	Endpoint(s)
Performance:  To obtain device-specific performance clinical data and to collect user feedback	
Primary Performance Endpoint: Percent of ‘yes’ responses to the binary question of: “Did UNITY VCS using vitreoretinal or combined surgical functionality perform per the intended use as defined in protocol Section 5.1?”

***Secondary Performance Endpoints:***

1. Total time in the eye  
From first entry into eye/first trocar in, to incision closure/last trocar out
2. Achievement of anatomical success at 3 months postop  
Percent of ‘yes’ responses to the question “Was anatomical success achieved for intended treatment (ex: macular hole closure, retinal attachment, etc. as applicable for the patient’s condition)?”
3. Change in BCDVA at 3 months postop when compared to preop

### 6.2 Secondary Objective(s)

Not Applicable

## 6.4 Safety Objective(s)

Table 6-2

Safety Objective(s)

Objective(s)	Endpoint(s)
To obtain device-specific safety clinical data	

• Ocular and nonocular AEs and SAEs

• Device deficiencies

• Secondary surgical interventions

• Unplanned intraoperative procedures

[figure not shown]
## 7 INVESTIGATIONAL PLAN

### 7.1 Study Design

This is a prospective, single arm, nonrandomized and multicenter clinical study in Australia (AUS) and/or the United States of America (USA) with approximately a 3-month follow-up.

Figure 7-1

Study Design Flow

### 7.2 Rationale for Study Design

The UNITY VCS is a Class IIb nonimplantable medical device in the EU and AUS and a Class II nonimplantable medical device in the USA. For this class category, there are no currently well-established study designs governed by health authorities or international standards. The prospective design of this traditional feasibility study will reduce sources of bias and confounding variables. The intended patient population represents the majority of patients that will require use of the investigational device for posterior segment surgery in the operating

room with or without simultaneous cataract surgery. The inclusion/exclusion criteria were carefully selected to reduce the likelihood of severely confounding the study outcomes.

The study design was also carefully thought out to allow it to represent a real world setting to ensure minimal intervention to the site's standard of care; this ensures the study gains the most realistic response regarding device performance and safety. [REDACTED]

[REDACTED]

[REDACTED]

A potential weakness of the current study design is the fact that it is a single arm study. However, this single arm design is justified given that there are well established data regarding safety and performance of vitreoretinal surgery as well as combined vitreoretinal and cataract surgery. As such, the safety and performance results from this study can be compared against this rich body of evidence to ensure the device meets state of the art standards.

### **7.2.1 Purpose and Timing of Interim Analyses and Resulting Design Adaptations**

Not applicable. There are currently no planned interim analyses.

### **7.3 Rationale for Duration of Treatment/Follow-up**

The follow-up schedule was designed to allow collection of data at key time points that yield relevant performance and safety outcomes. The follow-up period will allow for adequate safety monitoring of adverse events; if patients develop complications, those will typically be present within approximately 1 month of cataract surgery and 3-months of vitreoretinal surgery.

### **7.4 Rationale for Choice of Comparator Product**

There is no comparator in this study due to the nature of the study being a feasibility study.

### **7.5 Data Monitoring Committee**

Not applicable

## **8 STUDY POPULATION**

The study population will consist of male and female subjects (18 years or older) requiring posterior segment surgery in the operating room with or without simultaneous cataract surgery (unilaterally). It is aimed to enroll (consent) approximately 120 subjects in up to 8 sites in AUS and/or the USA with a target of 100 subjects treated, with approximately 10 to 40 subjects per

site. Site-specific targets may vary based upon individual site capabilities and each site may include more than one surgeon. Estimated time needed to recruit subjects for the study is approximately 3 months; however, unanticipated circumstances may shorten or lengthen this time and would not require amendment of this protocol. Because a 10% screening failure rate is expected and 10% for loss to follow-up, approximately 120 subjects are expected to be enrolled to ensure 100 completed subjects.

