Device Deficiency	
Inadequacy of a medical device with respect to its identity, quality, durability, reliability, usability, safety, or performance.
 
Note: This definition includes malfunctions, use errors, and inadequacy in the information supplied by the manufacturer including labelling related to the investigational medical device or the comparator.
 
Requirements for reporting device deficiencies in the study can be found in Section 11.

Enrolled Subject	Any subject who signs an ICF for participation in the study.
Point of Enrollment	The time at which, following recruitment and before any clinical investigation-related procedures are undertaken, a subject signs and dates the informed consent form.
Interventional Clinical Trial	A pre- or postmarket clinical investigation where the assignment of a subject to a particular medical device is decided in advance by a clinical investigation plan, or diagnostic or monitoring procedures requested in the CIP are in addition to those available as normal clinical practice and burden the subject.
Investigational Product	A preventative (vaccine), a therapeutic (drug or biologic), device, diagnostic, or palliative used as a test or comparator product in a clinical trial, including a product with a

	marketing authorization when used or assembled (formulated or packaged) in a way different from the authorized form, or when used for an unauthorized indication, or when used to gain further information about the authorized form.
Malfunction	Failure of an investigational medical device to perform in accordance with its intended purpose when used in accordance with the instructions for use or clinical investigation plan (CIP), or investigator's brochure (IB).
Nonserious Adverse Event	Adverse event that does not meet the criteria for a serious adverse event.
Serious Adverse Device Effect (SADE)	Adverse device effect that has resulted in any of the consequences characteristic of a serious adverse event.

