	
Planned number of subjects enrolled/consented: Approximately 120 subject eyes (unilateral subjects)
 
Planned number of completed subjects: Approximately 100 subject eyes (unilateral subjects)

Sites and Locations  (See Section 8.1 for a complete list of inclusion criteria)	
Planned number of clinical sites: up to 8 sites
 
Planned locations (initial list of locations, which may change during start up or conduct according to study needs): Australia and/or United States

Key inclusion criteria  (See Section 8.1 for a complete list of inclusion criteria)	

Adults <math>\geq</math> 18 years requiring posterior segment surgery in the operating room with or without simultaneous cataract surgery

Clear media except for cataract and vitreous hemorrhage

In simultaneous cataract and vitreoretinal surgery, eligible to undergo primary hydrophobic acrylic IOL implantation into the capsular bag

For those with planned simultaneous cataract and vitreoretinal surgery, keratometry of 41 to 46 D, anterior chamber depth of greater than 2.5 mm, and axial length of 22 to 28 mm

Key exclusion criteria  (See Section 8.2 for a complete list of exclusion criteria)	

Previous vitrectomy in the operative eye aside from those requiring silicone oil removal

Neovascular or uncontrolled glaucoma (IOP <math>></math> 21 mmHg despite maximally tolerated medications/surgical interventions)

Preoperative hypotony (<math><</math> 6 mmHg)

Planned glaucoma or postoperative surgeries during study aside from silicone oil removal (e.g., corneal refractive surgery)

Laser-assisted lens fragmentation

Inadequate pupil dilation (<math><</math> 6 mm)

Unpredictable cases that would severely confound the results of the study per investigator's clinical judgment (e.g., endophthalmitis, TASS, tumor, complex dislocated IOL, penetrating or severe ocular trauma such as globe rupture, zonular instability, pseudoexfoliation, use of systemic medications known to complicate surgery, Coat's disease, Vogt-Koyanagi-Harada disease, or Bechet's disease)

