## **10.2 Description of Study Procedures and Assessments**

Study-specific procedures and assessments described here may include standard of care; other standard of care procedures performed in the clinical management of the subject are not excluded.

Detailed descriptions of assessments and procedures are provided in the MOP. The investigator is responsible for ensuring responsibilities for all procedures and assessments are delegated to appropriately qualified site personnel.

The enrollment on this study is competitive and once the target number of subjects is achieved, sponsor will close the enrollment.

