7 SAMPLE SIZE AND POWER CALCULATIONS

Based on a sample of 100 surgeries, the expected half-width of the 95% confidence interval for the percentage of surgeons reporting 'yes' to the question "***Did UNITY VCS using vitreoretinal or combined surgical functionality perform per the intended use as defined in protocol Section 5.1?***" will be $1.96\sqrt{p(1-p)/100}$. This half-width is widest at $p = 50\%$. Under this conservative assumption, the expected half-width is < 10% given the sample size of 100.

Allow enrollment for an additional 10% for screen failure and 10% for loss to follow-up to ensure 100 completed subjects.

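### About 120 consented subjects do not ensure 100 completers: the plan's own rates give about 97, and its conflicting target of 100 treated gives about 90

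*Protocol*

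**What the plan says.** Protocol section 8 gives three totals in one paragraph. The consent total is "It is aimed to enroll (consent) approximately 120 subjects in up to 8 sites", and the same sentence continues "with a target of 100 subjects treated". The paragraph ends with the claim that "approximately 120 subjects are expected to be enrolled to ensure 100 completed subjects". The reason it gives for that number is a pair of rates: "Because a 10% screening failure rate is expected and 10% for loss to follow-up".

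The Protocol Summary (section 3) gives the completed figure as approximate: "Planned number of completed subjects: Approximately 100 subject eyes (unilateral subjects". SAP section 7 states the allowance as a mark-up: "Allow enrollment for an additional 10% for screen failure and 10% for loss to follow-up to ensure 100 completed subjects". Protocol section 12.8 and the sample size row of the Protocol Summary say the same.

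Three other provisions bear on the arithmetic:

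- The Glossary defines an enrolled subject as "Any subject who signs an ICF for participation in the study". Section 10.4.1 places screen failures after consent and before exposure to the device, so they are counted inside the 120.
- Section 10.4.2 does not allow discontinued subjects to be replaced.
- Section 10.2 describes competitive enrollment and says that "once the target number of subjects is achieved, sponsor will close the enrollment". It does not say which target is meant.

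**The concern.** There are two faults. First, the step from 100 to 120 adds 10% of 100 twice. The stated figures are rates that apply to larger groups: screen failure to those who consent, and loss to follow-up to those treated. Adding them to the number wanted at the end understates the number needed at the start. The documents then say that this number ensures the result.

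Second, 100 treated and 100 completed cannot both be the target when 10% of treated subjects are expected to be lost. Nothing in either document reconciles them, and the rule that closes enrollment depends on which one is meant.

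At stake are the two 3-month secondary endpoints, anatomical success and change in BCDVA. Both depend on subjects who reach the last visit, and no imputation is planned (Protocol 12.5, SAP 4.3).

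**Working it through.** **Inputs**

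- Consented: 120; treated target: 100; completed target: 100 (Protocol 3 and 8).
- Screen failure 10% and loss to follow-up 10% (Protocol 8, 12.8; SAP 7).
- Precision basis: 100 surgeries, half-width 1.96 × √(p(1 − p)/n), widest at p = 50% (Protocol 12.8, SAP 7).

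**The plan's own figure**

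100 × (1 + 0.10 + 0.10) = 120. This reproduces the stated total exactly.

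**Forward from 120 consented**

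- Treated: 120 × 0.90 = 108.
- Completed: 108 × 0.90 = 97.2.
- If both rates are taken on the 120 instead: 120 × 0.80 = 96.

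**Forward from 100 treated**

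- Completed: 100 × 0.90 = 90.
- Getting exactly 100 treated from 120 consented would need a screen failure rate of 1 − 100/120 = 16.7%, not 10%.

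**Backward from 100 completed**

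- 100 / (0.90 × 0.90) = 123.5, so 124 consented and about 112 treated (124 × 0.90 = 111.6).
- Rounding up at each step (100 → 112 → 125), or taking both rates on the consented number (100/0.80), gives 125.

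**Chance of at least 100 completers**

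This is the upper tail of a binomial distribution with completion probability 0.81, treating subjects as independent.

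| Consented | Expected completers | P(at least 100) |
|---|---|---|
| 120 | 97.2 | 0.30 |
| 124 | 100.4 | 0.59 |
| 130 | 105.3 | 0.90 |

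**Effect on precision**

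These are half-widths for a proportion at p = 50%, by the plan's formula.

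| n | Where it arises | Half-width |
|---|---|---|
| 108 | treated, from 120 consented | 9.4% |
| 100 | treated target, or completed target | 9.8% |
| 97 | completed, from 120 consented | 9.95% |
| 90 | completed, from 100 treated | 10.3% |

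**The case against.** The strongest reply is that little depends on the difference. The Protocol Summary calls both 120 and 100 approximate; 97.2 is 2.8% below 100, and 123.5 is 2.9% above 120. The additive mark-up is also stated openly. The only precision claim concerns the primary endpoint, which rests on surgeries and not on completers: with 120 consented, about 108 are treated, and the chance of at least 100 treated is about 99%. There is no hypothesis test, so no power is lost. No precision target is set for the 3-month endpoints, and going from 100 to 90 completers costs about half a percentage point of half-width (10.3% against 9.8%). The 30% figure uses a hard threshold; under the same model the chance of at least 95 completers is about 74%, and of at least 90 about 96%. Finally, enrollment means consent, so the closing rule may refer to the 120, in which case the 90 does not arise.

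Most of this stands as a limit on importance. It does not make the text correct. A figure that is missed about 70% of the time under the plan's own rates is not ensured. Approximate wording cannot merge treated and completed subjects, which are different groups separated by a stated 10% loss. The reading of the closing rule as 120 consented is possible but weak, because the only total that section 8 itself calls a target is the 100 treated.

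**Conclusion.** The concern holds. By the plan's own rates, 120 consented gives an expected 97.2 completers, with about a 30% chance of reaching 100. If enrollment closes at 100 treated, the expected number is 90. The 97 against 100 is a small shortfall with an overstated guarantee. The more serious fault is that two incompatible targets stand in one paragraph and the closing rule does not choose between them.

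The expected counts assume that screen failure applies to those who consent and loss to follow-up to those treated, as the documents' definitions imply. The probability also assumes that subjects are independent and that 81% is the true completion rate. The primary endpoint's statement of a half-width below 10%, by the plan's formula, is unaffected at 100 or 108 surgeries. The effect is confined to the 3-month endpoints and to the operation of the closing rule. This should be corrected, but it does not threaten the study's main result.

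**What to change.** Give the same figures in Protocol sections 3, 8 and 12.8 and SAP section 7. For example: about 120 consented, about 108 treated (the basis for the primary endpoint) and about 97 completed (the basis for the 3-month endpoints). Replace the guarantee of 100 completers, and the separate target of 100 treated, with one defined target, and name it in Protocol 10.2 as the number that closes enrollment.

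Done this way the change is wording only and needs no additional subjects; the cost is a slightly less favourable stated number of completers. If 100 completers is a firm requirement, plan for 124 consented, four more than now. That makes 100 the expected number, with about a 59% chance of reaching it; about 130 consented would raise the chance to 90%.

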## 8.1 Inclusion Criteria

Written informed consent must be obtained before any study specific assessment is performed. Upon signing informed consent, the subject is considered enrolled in the study.

Subjects eligible for inclusion in this study must fulfill **all** of the following criteria:

1. Subject must be able to understand and sign an IRB/IEC approved informed consent form.
2. Willing and able to attend all scheduled study visits as required per protocol.
3. Adults  $\geq$  18 years requiring posterior segment surgery in the operating room without or with simultaneous cataract surgery
4. Clear media except for cataract and vitreous hemorrhage
5. In simultaneous cataract and vitreoretinal surgery, eligible to undergo primary hydrophobic acrylic IOL implantation into the capsular bag
6. For those with planned simultaneous cataract and vitreoretinal surgery, keratometry of 41 to 46 D
7. For those with planned simultaneous cataract and vitreoretinal surgery, with following biometry, anterior chamber depth of greater than 2.5 mm, and axial length of 22 to 28 mm

## 8.2 Exclusion Criteria

Subjects fulfilling **any** of the following criteria are not eligible for participation in this study.

1. Women of childbearing potential, defined as all women who are physiologically capable of becoming pregnant and who are not postmenopausal for at least 1 year or are less than 6 weeks since sterilization, are excluded from participation if any of the following apply:
  - a. they are currently pregnant,

- b. have a positive urine pregnancy test result at Screening,
- c. intend to become pregnant during the study period,
- d. are breastfeeding.

Subjects who become pregnant during the study will not be discontinued; however, data will be excluded from the effectiveness analyses because pregnancy can alter refraction and visual acuity results.

2. Previous vitrectomy in the operative eye aside from those requiring silicone oil removal
3. Neovascular or uncontrolled glaucoma (IOP > 21 mmHg despite maximally tolerated medications/surgical interventions)
4. Preop hypotony (<6 mmHg)
5. Planned glaucoma or postoperative surgeries during study aside from silicone oil removal (e.g., corneal refractive surgery)
6. Laser-assisted lens fragmentation
7. Inadequate pupil dilation (< 6 mm)
8. Unpredictable cases that would severely confound the results of the study per investigator's clinical judgment (e.g., endophthalmitis, TASS, tumor, complex dislocated IOL, penetrating or severe ocular trauma such as globe rupture, zonular instability, pseudoexfoliation, use of systemic medications known to complicate surgery, Coat's disease, Vogt-Koyanagi-Harada disease, or Bechet's disease)
9. Currently participating in another drug or device clinical trial, or having participated in another drug or device clinical trial within 30 days of enrolment into this study

